2.4.1. Subgroups for Efficacy Analyses

- Sex: Male, Female
- Age categories: ≤ 45 years, > 45 years
- Race: Asian, non-Asian
- Geographical region: Asia, Europe, North America, South America
- Has never received HBV treatment (only currently not treated):
 - Yes
 - No
- Type of NA at study entry (only for virologically suppressed participants):
 - Tenofovir Disoproxil Fumarate (TDF)
 - Tenofovir Alafenamide Fumarate (TAF)
 - Entecavir (ETV)
- Hepatitis B e Antigen (HBeAg) status at screening (qualitative):
 - Positive

- Negative
- Treatment history:
 - Currently not being treated
 - Virologically suppressed
- HBsAg level at baseline:
 - <1,000 IU/mL
 - ≥1,000 IU/mL-<10,000 IU/mL
 - ≥10,000 IU/mL
- HBV DNA level at baseline (only for currently not treated):
 - <100,000 IU/mL
 - ≥100,000 IU/mL
- HBV RNA level at baseline:
 - < 1,000 copies /mL
 - ≥1,000-<10,000 copies /mL
 - ≥10,000 copies /mL
- HBcrAg level at baseline:
 - <3 log U/mL
 - ≥3 log U/mL-<4 log U/mL
 - ≥4 log U/mL
- HBsAg Antibody (Anti-HBs) level at baseline:
 - <10 mIU/mL
 - ≥10 mIU/mL
- Alanine Transferase (ALT) at baseline: ≤ 1.0 ULN, > 1.0 ULN - <2.5 ULN, ≥ 2.5 ULN
- HBV genotype assessed at screening and tested using the INNO-LiPA or sequence based HBV genotyping data: Genotype A, B, C, D, E, F, G, H, I, J and Unknown
- Combination of HBeAg status at screening and treatment history:
 - Positive/Currently not being treated
 - Positive/Virologically suppressed
 - Negative/Currently not being treated
 - Negative/Virologically suppressed
- Combination of HBeAg status at screening and age categories:
 - Positive/≤ 45 years
 - Positive/> 45 years
 - Negative/≤ 45 years

- Negative/> 45 years
- Combination of HBeAg status at screening and HBsAg level at baseline:
 - Positive/<1,000 IU/mL
 - Positive/ \geq 1,000 IU/mL-<10,000 IU/mL
 - Positive/ \geq 10,000 IU/mL
 - Negative/<1,000 IU/mL
 - Negative \geq 1,000 IU/mL-<10,000 IU/mL
 - Negative \geq 10,000 IU/mL
- Combination of treatment history and age categories:
 - Currently not being treated \leq 45 years
 - Currently not being treated $>$ 45 years
 - Virologically suppressed \leq 45 years
 - Virologically suppressed $>$ 45 years
- Combination of treatment history and HBsAg level at baseline:
 - Currently not being treated <1,000 IU/mL
 - Currently not being treated \geq 1,000 IU/mL-<10,000 IU/mL
 - Currently not being treated \geq 10,000 IU/mL
 - Virologically suppressed <1,000 IU/mL
 - Virologically suppressed \geq 1,000 IU/mL-<10,000 IU/mL

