4.2.2. Baseline Characteristics

For the viral activity parameters (e.g. HBeAg, HBsAg, HBV DNA, HBV RNA, HBcrAg, anti-HBs antibody, anti-HBe antibody), baseline values are used unless specified differently.

- Duration of HBV infection (Years) = (date of randomization – date of HBV infection +1)/365.25; rounded to 1 decimal
- Time since HBV diagnosis (Years) = (date of randomization – date of HBV diagnosis+1)/365.25; rounded to 1 decimal
- Mode of HBV infection: Sexual transmission, intravenously injectable drug use, blood transfusion, Hemophilia-associated injection, occupational exposure, mother to child transmission, unknown and other
- Treatment history: not currently treated, virologically suppressed
- History of IFN-alpha (All participants): Yes, No
- History of Lamivudine, Telbivudine, Adefovir (All participants): Yes, No
- Has never received HBV treatment (only for currently not treated participants): Yes, No
- Type of NA at study entry (only for virologically suppressed participants): TDF, TAF, ETV
- HBeAg status at screening: positive, negative
- HBeAg at baseline (quantitative): values in IU/mL and log10 IU/mL (for HBeAg positive participants only)
- HBsAg at baseline (quantitative): values in IU/mL and log10 IU/mL
- HBsAg category at baseline (quantitative: IU/mL):
 - Participants with HBsAg <500 IU/mL
 - Participants with HBsAg <1,000 IU/mL
 - Participants with HBsAg <10,000 IU/mL
 - Participants with HBsAg $\geq 10,000$ IU/mL
- HBV DNA at baseline (quantitative): values in IU/mL and log10 IU/mL
- HBV DNA category at baseline (quantitative: IU/mL):
 - Participants with HBV DNA < LLOQ (20 IU/mL) target detected (TD) or target not detected (TND)
 - Participants with HBV DNA < LLOQ (20 IU/mL) target detected
 - Participants with HBV DNA < LLOQ (20 IU/mL) target not detected

- Participants with HBV DNA < 60 IU/mL
- Participants with HBV DNA < 2,000 IU/mL
- Participants with HBV DNA < 20,000 IU/mL
- Participants with HBV DNA < 100,000 IU/mL
- Participants with HBV DNA \geq 100,000 IU/mL
- HBV RNA (quantitative): values in copies/mL and log10 copies/mL
- HBV RNA category at baseline (quantitative: copies/mL):
 - Participants with HBV RNA TND
 - Participants with HBV RNA < limit of detection (LOD)
 - Participants with HBV RNA < 1000 copies /mL
 - Participants with HBV RNA < LLOQ
 - Participants with HBV RNA \geq LLOQ
- Hepatitis B core related antigen (HBcrAg) at baseline (quantitative): values in log U/mL

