5.4.5. HBsAg, HBeAg, and HBV DNA

5.4.5.1. Values and Changes Over Time

HBsAg and HBeAg will be summarized by treatment history (not currently treated and virologically suppressed) and overall, and HBV DNA will only be summarized by treatment history.

Descriptive statistics on actual values (original unit and log10 transformed values) and changes from baseline (log10 transformed values) over time in HBsAg, HBeAg and HBV DNA will be summarized by intervention arm. Mean (+/- SE) plots of the actual values and the change from baseline (log10 transformed) will be presented over time per blood marker by intervention arm.

In addition, the change from baseline value to nadir (i.e. maximum decrease for each participant) in each blood marker will be summarized descriptively by intervention arm. Box plots of the changes to nadir in HBsAg, HBeAg, and HBV DNA will display the distribution by intervention arm.

Change from baseline based on log10 transform for quantitative HBsAg, HBeAg and HBV DNA will be analyzed using mixed effects model for repeated measures [MMRM]) including intervention arm, analysis time point (week), and 2 randomization stratification factors (HBeAg status at screening [positive versus negative] and treatment history [not currently treated versus virologically suppressed]) and baseline blood marker categorical variable as fixed effects. In addition, the above model will be augmented with an intervention arm-by-analysis week interaction term (i.e. treatment-by-time interaction term) to evaluate the change of treatment effect over time and the intervention arm-by-baseline interaction term. The covariance structure will include a random intercept at the level of the participant to capture between-participant variability, while within-participant variability will be captured with an unstructured (type=UN) covariance matrix. In case of convergence problems, simpler variance-covariance structures such as Toeplitz or AR (1) will be considered. The selection of any of these structures will be determined after exploration of the observed correlation structure. The LS mean of change from baseline, standard error (SE), 90% confidence interval (CI) and p-values will be provided.

Descriptive statistics on actual values (original unit and log10 transformed values) and changes from baseline (log10 transformed values) at end of treatment in HBsAg, HBeAg and HBV DNA, respectively, will be summarized by study intervention arm by outcome response (i.e. by NA

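### The MMRM of change in log10 HBsAg, HBeAg and HBV DNA adjusts for a categorised baseline with no defined categories, where continuous log10 baseline is available and, under an approximately linear relation, at least as precise

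*SAP*

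**What the plan says.** SAP Section 5.4.5.1 states: "Change from baseline based on log10 transform for quantitative HBsAg, HBeAg and HBV DNA will be analyzed using mixed effects model for repeated measures". The fixed effects are arm, week, the two randomisation stratification factors and, last in the list, "baseline blood marker categorical variable as fixed effects". The model is then extended with an arm-by-week term and "the intervention arm-by-baseline interaction term". The section does not say why the baseline is categorised or where the cut-offs lie.

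The continuous values exist. SAP Section 4.2.2 lists "HBsAg at baseline (quantitative): values in IU/mL and log10 IU/mL" and "HBV DNA at baseline (quantitative): values in IU/mL and log10 IU/mL", and the same for HBeAg in HBeAg-positive participants.

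Other parts of the SAP do not supply usable categories for this model:
- Section 2.4.1, on subgroups, cuts "HBsAg level at baseline" at 1,000 and 10,000 IU/mL. It cuts HBV DNA at 100,000 IU/mL, but only for participants not currently treated. It has no HBeAg level categories.
- The HBsAg and HBV DNA categories in Section 4.2.2 overlap (for example below 500, below 1,000 and below 10,000 IU/mL for HBsAg), so they cannot serve as levels of a factor. It has no HBeAg level categories either.

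Elsewhere the SAP keeps baseline continuous: in the multiple imputation models (Section 5.2.2.1.4), the fibrosis ANCOVA (Section 5.5.1) and the HBQOL ANCOVA (Section 9.1).

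**The concern.** The response is a change score on a continuous log10 scale. If change depends on baseline, a category term removes only the between-category part of that dependence. The rest stays in the residual and widens the confidence intervals for arm differences. The comparisons with Arms 5 and 6, planned at 45 participants each, have least precision to spare.

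Because no categories are defined, an analyst also has to choose cut-offs before fitting the model, and for HBeAg the SAP offers no starting point. The arm-by-baseline term adds to this: with six arms and three categories it takes (6-1) x (3-1) = 10 degrees of freedom, against 5 for a continuous baseline.

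**Working it through.** The plan gives no standard deviation, correlation, power or sample size for this model, so there is no stated figure to reproduce. The size has to be shown as a range over assumptions.

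**Inputs from the documents.** HBsAg cut-offs of 1,000 and 10,000 IU/mL, which are 3 and 4 on the log10 scale (SAP 2.4.1, borrowed because the model has none of its own). HBV DNA cut-off of 100,000 IU/mL, log10 5, untreated participants only. Arm sizes of 90 and 45 (SAP 1.4).

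**Assumed.** Normal log10 baseline; linear relation of change to baseline; a single visit; no arm-by-baseline term; no other covariates. HBsAg mean 3.3 to 4.0 and SD 0.5 to 0.9. HBV DNA in untreated participants, mean 4.5 to 6 and SD 1.2 to 1.8. The correlation rho between baseline and change is varied. Only its square matters, so the sign is irrelevant.

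**Step 1: share of baseline variance kept by the categories.** R is the sum over categories of p x m², where p is the category's probability and m its mean on the standardised scale. Example: mean 3.5, SD 0.7. The cuts are at z = -0.714 and +0.714. Each tail has p = 0.2375 and |m| = 0.3091/0.2375, and the middle category has m = 0. So R = 2 x 0.3091²/0.2375 = 0.805. Over the whole assumed range, R is 0.70 to 0.81 for HBsAg in three categories and 0.49 to 0.64 for HBV DNA in two.

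**Step 2: variance of the arm difference, categorical against continuous adjustment.** Ratio = (1 - rho² x R)/(1 - rho²). In the example at rho = 0.5: (1 - 0.25 x 0.805)/0.75 = 1.065. The confidence interval widens by the square root of the ratio.

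| rho | HBsAg: variance larger by | HBsAg: interval wider by |
|---|---|---|
| 0 | 0% | 0% |
| 0.3 | 2-3% | 1.0-1.5% |
| 0.5 | 6-10% | 3-5% |
| 0.7 | 18-29% | 9-14% |

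**Step 3: simulation check.** A 90 against 45 ANCOVA (mean 3.5, SD 0.7, 3,000 runs) gave ratios of 1.00, 1.02, 1.07 and 1.20 at rho 0, 0.3, 0.5 and 0.7. The formula gives 1.00, 1.02, 1.07 (1.065) and 1.19. In the same runs the ratio with no baseline adjustment at all was 1.36 at rho 0.5 and 1.91 at rho 0.7. Three categories therefore already recover most of the available gain.

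**Step 4: HBV DNA in untreated participants.** Entry requires at least 2,000 IU/mL (HBeAg-negative) or 20,000 IU/mL (HBeAg-positive) (protocol 5.1). Values below LLOQ are set to 15 or 5 IU/mL (SAP Table 3), which is log10 1.18 or 0.70. For a participant who reaches that floor, change equals a near-constant minus baseline, so rho moves towards -1 as more participants reach it. With two categories the variance is 4-5% larger at rho 0.3, 12-17% at 0.5, 35-49% at 0.7, and 2.5 to 3.2 times as large at 0.9.

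**The case against.** The case for categories is not empty.

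- Categories do not assume linearity. Pooled baseline HBV DNA is far from normal: suppressed participants enter below 60 IU/mL, many with values imputed at the floor, while untreated participants enter at 2,000 IU/mL or more. This stands, mainly for HBV DNA. A below-LLOQ indicator, a flexible term or separate fits by treatment history would meet it. A reader might infer that categorising has no benefit and that changing it has no downside; the documents do not support either inference.
- A categorical arm-by-baseline term gives arm effects by baseline level without assuming linear effect modification, in line with the planned subgroups. This is a defensible preference, though the SAP does not state it. The formula above leaves this interaction out.
- The stratification factors are already in the model and carry some baseline information, especially for HBV DNA, so the loss in the actual model may be smaller than shown.
- A baseline-by-week term would add 14 slopes over the 15 post-baseline double-blind visits, to a model with an unstructured covariance for which the SAP already foresees convergence trouble. This is fair, so the term should be conditional on convergence.
- SAP Amendment 2 (19 May 2022) follows interim analyses already done, so a new covariate form would be chosen after data had been seen. This does not bear on whether the method is better, but the change would have to be declared.

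**Conclusion.** The point holds as a modest, optional improvement. The baseline term is categorical, unexplained and without defined levels for this model, while the continuous log10 value is collected. Under an approximately linear relation the continuous form is at least as precise, apart from negligible degrees-of-freedom effects.

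The size is not fixed by the documents. For HBsAg it runs from nil to the 18-29% of variance shown at correlation 0.7, and no passage supports any particular correlation. A reader might take one narrow figure for the loss; that would rest entirely on an assumed distribution, number of categories and correlation. For untreated HBV DNA the loss could be larger, on the floor argument.

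A reader might also infer bias, or a threat to the trial's main conclusions. Neither follows. Baseline differences left within categories are chance imbalance in a stratified randomised trial. The analysis is an other secondary one with 90% intervals and no multiplicity adjustment (SAP 5.1.1 and 5.4). The primary and key secondary tests use binary endpoints and are unaffected.

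**What to change.** In SAP Section 5.4.5.1:

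1. Replace the categorical baseline with continuous log10 baseline of the same marker, and add baseline-by-week if the model converges.
2. Use the same continuous baseline in the arm-by-baseline term, and report arm effects at the mean baseline.
3. For HBV DNA, add a below-LLOQ indicator or a flexible baseline term, or fit the model within treatment-history groups.
4. Keep the baseline categories for subgroup displays.

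The cost is a linearity assumption and a few extra model terms. Because interim data have been analysed, date the change and report the categorical version, with its cut-offs stated, as a sensitivity analysis. If the sponsor prefers to keep categories, the minimum is to define them for each marker and give the reason.

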Blood chemistry (including liver function tests) ^{u,v,w}	X	X	X	X	X	X	X	X	X	X	X	X	X	X	X	X	X
Blood coagulation	X	X			X		X	X	X	X	X	X	X	X	X	X	X
Urinalysis and urine chemistry ^x	X	X			X		X	X	X	X	X	X	X	X	X	X	X
Urine pregnancy test (women of childbearing		X			X		X	X	X	X	X	X	X	X	X	X	X
potential)																	
Renal biomarkers ^y		X						X			X			X			X
AFPw	X										X						X
Efficacy Evaluations																	
Fibroscan		(X) ^z															
HBV Virology																	
Blood sampling for HBV DNA	X	X	X	X	X	X	X	X	X	X	X	X	X	X	X	X	X
Blood sampling for HBV RNA ^{aa}	X	X	X	X	X		X	X	X	X	X		X		X		X
Sampling for viral genome sequencingbb	X	X			X		X	X		X	X		X		X		X
HBV Serology																	
Blood sampling for:																	
Anti HBs and anti HBe	X	X									X						X
HBsAg and HBeAgcc (qualitative)	X										X						X
HBsAg (quantitative)	X	X	X	X	X	X	X	X	X	X	X	X	X	X	X	X	X
HBeAg ^{dd} (quantitative)	X	X		X	X		X	X	X	X	X		X		X	X	X
HBcrAg ^{aa}	X	X		X	X		X	X		X	X		X		X	X	X
Exploratory serologyee	X	X		X	X		X	X	X	X	X		X		X	X	X
Pharmacokinetics																	
Blood sampling for sparse PK of JNJ 3989, JNJ 6379, and/or NA ^{ff}		Xgg			Xgg			Xgg			Xgg						X ^{hh}
Blood sampling for intensive PK of JNJ 3989, JNJ 6379, and/or NA (PK subgroup) ⁱⁱ					X												
Exploratory Biomarkers																	
Whole blood RNA gene expression		X						X			X						X
Whole blood single cell profiling		X	X		X		X	X			X			X			X
Host serum proteins (eg, cytokines)		X	X	X	X		X	X			X		X		X		X
Antidrug antibodies (to JNJ 3989)		X					X		X		X		X		X		
Immune Monitoring																	
Immune cells (PBMCs) (selected sites only) ^{ij}		X									X						X

Study Phase	Screeninga	Double-blind Study Intervention ^b															
Visit Day (D)/Week (W)	W 4 to 0 ^d	D1e	W1	W2	W4	W6	W8	W12	W16	W20	W24	W28	W32	W36	W40	W44	W48/WDc
Study Day (Window)	28	1	8 +/ 2d	15 +/ 2d	29 +/ 2d	43 +/ 2d	57 +/ 2d	85 +/ 2d	113 +/ 3d	141 +/ 3d	169 +/ 3d	197 +/ 3d	225 +/ 3d	253 +/ 3d	281 +/ 3d	309 +/ 3d	337 +/ 3d
Pharmacogenomics (DNA)																	
Exploratory host genotyping (optional)kk		X															
PRO Evaluations ^{II}																	
HBQOL		X						X			X			X			X
HBV specific self stigma	X	X						X			X			X			X
PGIC								X			X			X			X
Ongoing Participant Review																	
Concomitant therapy	X	X	X	X	X	X	X	X	X	X	X	X	X	X	X	X	X
Adverse events	X	X	X	X	X	X	X	X	X	X	X	X	X	X	X	X	X

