1.3.2. Schedule of Activities – Follow-up Phase

After study intervention completion (or early discontinuation), all participants will enter the 48-week follow-up phase (unless they withdraw consent). In the control arm (Arm 6), the study visit frequency in this follow-up phase is lower than in Arms 1 to 5. Note that the participants in Arms 1 to 6 completing NA treatment at Week 48 will also follow a more frequent visit schedule with a study visit at least once every 4 weeks. In case NA re-treatment criteria are met, participants will switch to less frequent follow-up, provided that their HBV DNA and ALT values are stable.

The follow-up phase will be extended to 48 weeks after the end of NA treatment for participants who stop NA treatment during the follow-up phase based on meeting the NA treatment completion criteria. The visit frequency of participants from Arm 6 who enter the extended follow-up phase will be increased to match that of participants that enter the extended follow-up coming from Arms 1 to 5. In case NA re-treatment criteria are met, participants will switch to less frequent follow-up, provided that their HBV DNA and ALT values are stable.

The visit frequency during the follow-up phase and the extended follow-up phase is provided below for all intervention arms.

Study Phase		Follow-up ^{a,b}														
Follow up (FU) Week (W)		FU W4	FU W6	FU W8	FU W12	FU W16	FU W20	FU W24	FU W28	FU W30	FU W32	FU W36	FU W40	FU W42	FU W44	FU W48 EOS
FU Study Day (Window)	15 +/ 4d	29 +/ 4d	43 +/ 4d	57 +/ 4d	85 +/ 4d	113 +/ 4d	141 +/ 4d	169 +/ 4d	197 +/ 4d	211 +/ 4d	225 +/ 4d	253 +/ 4d	281 +/ 4d	295 +/ 4d	309 +/ 4d	337 +/ 4d
Visits in Intervention Arms 1 to 6 (NA stopped) ^c	X	X	X	X	X	X	X	X	X		X	X	X		X	X
Visits in Intervention Arms 1 to 5 (NA continued)	X	X	X	X	X	X	X	X		X		X		X		X
Visits in Intervention Arm 6 (NA continued)					X			X				X				X
Extended Follow up (Ext FU) in participants who complete NA treatment during follow up ^d	Ext FU W2	Ext FU W4	Ext FU W6	Ext FU W8	Ext FU W12	Ext FU W16	Ext FU W20	Ext FU W24	Ext FU W28	Ext FU W30	Ext FU W32	Ext FU W36	Ext FU W40	Ext FU W42	Ext FU W44	Ext FU W48 EOS
Ext FU Study Day (Window)	15 +/ 4d	29 +/ 4d	43 +/ 4d	57 +/ 4d	85 +/ 4d	113 +/ 4d	141 +/ 4d	169 +/ 4d	197 +/ 4d	211 +/ 4d	225 +/ 4d	253 +/ 4d	281 +/ 4d	295 +/ 4d	309 +/ 4d	337 +/ 4d
Visits in Interventions Arms 1 to 6 (NA stopped)	X	X	X	X	X	X	X	X	X		X	X	X		X	X
Visits in Interventions Arms 1 to 6 (NA re-started)	X	X	X	X	X	X	X	X		X		X		X		X

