1.5. Randomization and Blinding

Randomization

Central randomization is implemented in this study. Participants are randomly assigned to 1 of 6 intervention arms with a ratio of 2:2:2:2:1:1 (Arms 1:2:3:4:5:6). The randomization is stratified by HBeAg status at screening (positive versus negative) and by treatment history (not currently treated versus virologically suppressed).

Blinding

At Week 48 or earlier at the time of treatment discontinuation, it will be communicated to the investigators whether the participants were allocated to either an intervention arm (Arms 1 to 5) or the control arm (Arm 6) to determine which follow-up visit schedule will be followed. Only at Week 72, randomization codes (for Arms 1 to 5) will be fully disclosed to the investigators. The sponsor will be fully unblinded at the time of the primary analysis (all participants have completed Week 48 or discontinued early).

Sponsor personnel involved in the pharmacokinetic and pharmacodynamic modelling will have access to the pharmacokinetic and pharmacodynamic data before formal unblinding for the primary analysis. Sponsor personnel involved in trial conduct, data management, and statistics will not have access to these data prior to the primary analysis. The sponsor will be fully unblinded at the time of the primary analysis which will be conducted at the time when all participants have completed Week 48 or discontinued earlier.

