5.4. Other Secondary Endpoints

Statistical comparisons of all other secondary endpoints among intervention arms will be done with no adjustment for multiplicity.

In addition, the potential association between treatment outcome and baseline factors will be explored by multivariate logistic regression model in a similar fashion as described in Section 5.2.5.

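### The repeated-measures model for marker change pairs a participant random intercept with an unstructured covariance, which leaves one parameter inestimable, and convergence problems lead to an unordered fallback chosen after seeing the correlations

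*SAP*

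**What the plan says.** SAP 5.4.5.1 (Values and Changes Over Time) analyses log10 change from baseline in quantitative HBsAg, HBeAg and HBV DNA with a mixed model for repeated measures. It reports LS means, SEs, 90% CIs and p-values.

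- **Covariance.** The structure is to "include a random intercept at the level of the participant to capture between-participant variability, while within-participant variability will be captured with an unstructured (type=UN" matrix.
- **Fallback.** If convergence problems arise, "simpler variance-covariance structures such as Toeplitz or AR (1) will be considered". On how to choose among them: "The selection of any of these structures will be determined after exploration of the observed correlation structure". No order, criterion or trigger beyond convergence problems is given. The section does not say whether the random intercept stays in the model under a fallback.
- **Mean model.** A model with arm, week, the stratification factors and baseline category comes first. Then "the above model will be augmented with an intervention arm-by-analysis week interaction term" and an arm-by-baseline term. The section does not say which of the two supplies the reported LS means.
- **Blinding.** SAP 1.5: "The sponsor will be fully unblinded at the time of the primary analysis". The interim analyses in SAP 3.1 all come later.
- **Status.** SAP 5.4: "Statistical comparisons of all other secondary endpoints among intervention arms will be done with no adjustment for multiplicity".

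**The concern.** An unstructured matrix already allows every variance and covariance to take its own value, so it contains the between-participant component. A random intercept adds one constant to every element, and an unstructured matrix plus a constant is another unstructured matrix. The data therefore cannot divide the constant between the two parts, and the information matrix is singular by construction.

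This matters because of what follows a convergence problem. The analyst then picks a structure from an open list after viewing the data, at a time when treatment codes are known to the sponsor. If the intercept is kept, Toeplitz, the first fallback named, carries the same redundancy. The structure chosen determines the SEs, CIs and p-values reported for marker kinetics, which serve a stated secondary objective.

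**Working it through.** The plan gives no figure to reproduce on this point. The check has two parts.

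**1. Is the covariance model identified?**

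Inputs: the SAP does not list the visits that enter the model, so all scheduled post-baseline double-blind visits are assumed. Protocol 1.3.1 gives 15 for HBsAg and HBV DNA (Weeks 1, 2, 4, 6, 8, then every 4 weeks from 12 to 48). It gives 11 for quantitative HBeAg (Weeks 2, 4, 8, 12, 16, 20, 24, 32, 40, 44, 48).

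Formula: V = s·J + R, where J is the all-ones matrix, s the intercept variance and R the within-participant matrix. With T visits an unstructured R has T(T+1)/2 parameters: 15·16/2 = 120 and 11·12/2 = 66. The intercept adds one. The number of estimable parameters is the rank of the derivative of V with respect to all of them.

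| Structure plus intercept | 15 visits: parameters / rank | 11 visits: parameters / rank |
|---|---|---|
| Unstructured | 121 / 120 | 67 / 66 |
| Toeplitz | 16 / 15 | 12 / 11 |
| AR(1) | 3 / 3 | 3 / 3 |

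A likelihood check agrees. With 90 simulated participants and 4 visits, the log-likelihood was -112.4859 for s = 0, 0.1, 0.3 and 0.5 when R was lowered by the same amount. With 450 simulated complete participants and 15 visits, fits from four starting values all converged to the same objective (-3033.706) and the same Week 48 variance (1.009). Their intercept variances were 0.0009, 0.341, 0.478 and 0.533. The ratio of smallest to largest eigenvalue of the information matrix was 6e-18 with the intercept and 3.7e-6 without it. These fits were not run in SAS.

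HBeAg has the most parameters relative to participants. Footnote dd of Protocol 1.3.1 restricts quantitative HBeAg on treatment to participants HBeAg-positive at screening. From Protocol 4.1, the untreated HBeAg-positive group is 450 × 0.40 × 0.40 = 72, plus an unstated number of suppressed participants. That is about 14 untreated participants per 90-participant arm (72 × 90/450) and 7 per 45-participant arm.

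**2. What would the fallback do to the Week 48 SE?**

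Assumptions, none of them in the documents: the SD of change rises from 1 at the first visit to r, either linearly to Week 48 or levelling off at Week 12. The correlation is f + (1 - f)·exp(-gap/τ), with (τ, f) = (20, 0.5), (20, 0) and (40, 0.3). Data are complete and means are fitted by arm and week.

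Method: take the structure V minimising log|V| + tr(V⁻¹Σ), where Σ is the assumed covariance. The ratio of model SE to true SE is √(V₄₈/Σ₄₈). A nominal one-sided 0.05 test then runs at Φ(-1.645 × ratio).

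| Equal-variance Toeplitz or AR(1), 15 visits | SE ratio, r = 1.5 | SE ratio, r = 3 | Actual level, range over r |
|---|---|---|---|
| Levels off at Week 12 | 0.892-0.912 | 0.821-0.851 | 0.067-0.088 |
| Linear to Week 48 | 0.826-0.835 | 0.681-0.706 | 0.085-0.131 |

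The SE is thus 9-18% or 17-32% too small. At the HBeAg visits the figures are 8-17% and 16-31%. At r = 1 the ratio is 1.00.

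Heterogeneous-variance fallbacks err the other way. At 15 visits heterogeneous Toeplitz and AR(1) give ratios of 1.106-1.132 (actual level 0.031-0.034), and at the HBeAg visits 1.017-1.053. This holds at every r, including 1, because visit gaps of 1, 2, 2, 2 and then ten of 4 weeks are treated as equal. Sandwich SEs address this. Uncorrected ratios were 0.989 (45 vs 45 participants), 0.938 (14 vs 7) and 0.925 (7 vs 7). With the Kauermann-Carroll small-sample correction they were 0.999-1.000.

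**The case against.** The strongest reply is that the redundancy has not been shown to alter any reported number. The marginal covariance stays identified, the trial fits all converged, and software often sets the redundant variance to zero. All of that stands. A reader might infer that the LS means or SEs are biased as specified, or that the model will fail; the documents support neither.

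The SE errors are conditional. They need non-convergence, an equal-variance structure and growing spread. The SAP's list does not exclude heterogeneous versions, and looking at the data might reveal growing variance. With constant spread the named fallbacks show no such error, while heterogeneous ones without sandwich SEs would be worse. AR(1) with an intercept is identified, so only one of the two named fallbacks repeats the problem. Choosing a covariance from observed correlations is also common and is not selection on the treatment effect. These points limit the size of the concern. They do not supply an order, a trigger or a statement about the intercept.

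Follow-up schedules differ by arm and NA status; Protocol 1.3.2 says "In the control arm (Arm 6), the study visit frequency in this follow-up phase is lower than in Arms 1 to 5". A reader might infer that pairs such as Follow-up Weeks 28 and 42 are never scheduled for the same participant. The documents do not support this, because participants who meet the NA re-treatment criteria switch schedule (Protocol 1.3.2 and its footnote c). Those covariances are thinly supported, not empty.

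On the two mean models, the SAP does give a purpose for the augmented one, namely how the treatment effect changes over time. It still does not say which model is reported.

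**Conclusion.** The covariance specification is wrong as written: one parameter is inestimable at any number of visits, and this needs no assumption. The consequence is modest. Where the fit converges, results equal those of the unstructured model alone. The risk is an avoidable convergence failure, of unknown probability, that hands the SEs, 90% CIs and p-values to a choice made after unblinding. If that choice were an equal-variance structure and the SD of change grew 1.5- to 3-fold, the Week 48 SE would be about 9-32% too small. That range rests on assumed growth and correlation patterns and on all scheduled double-blind visits entering the model. The primary and key secondary tests do not use this model. The point is worth correcting but does not threaten the trial's main conclusions.

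**What to change.** Amend SAP 5.4.5.1 as follows.

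1. Drop the random intercept and use the unstructured covariance alone as the primary structure.
2. Prespecify the fallback order, without a random intercept: heterogeneous Toeplitz, then heterogeneous AR(1). Move down only on non-convergence or a non-positive-definite Hessian, and report the structure used.
3. Use empirical (sandwich) SEs in the fallbacks, preferably with a small-sample correction such as Kauermann-Carroll, because visit spacing is unequal and HBeAg numbers per arm are small.
4. State that the model with the arm-by-week term supplies the by-week LS means, 90% CIs and p-values.

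Restricting the follow-up model to visits common to the schedules being compared is optional. It would avoid thinly supported covariances, at the price of leaving some visits to the descriptive summaries.

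The cost is SAP wording; no new data are needed. One limit remains: sandwich SEs do not correct bias in the LS means if the fallback covariance is wrong and data are missing at random.
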